## Introduction:

Approximately 4.8 to 6.4 million Americans, comprising 30-40% of the U.S. diabetic population, exhibit symptomatic diabetic peripheral neuropathy (Harris, Eastman et al. 1993; Martyn and Hughes 1997; Apfel 1999). The prevalence may be as high as 50% in diabetics over 60 years of age. Up to 20% of the elderly population may be affected by peripheral neuropathies (PN) (Harris, Eastman et al. 1993; Richardson and Ashton-Miller 1996). Epidemiological evidence has linked PN patients to an increased risk of falling (Richardson, Ching et al. 1992; Richardson and Hurvitz 1995) and decreased stability while standing (Geurts, Mulder et al. 1992) and when exposed to external postural perturbations (Inglis, Horak et al. 1994). Consequently, there is a need for developing cost-effective interventions for improving mobility and balance to manage fall risk in the elderly (Rubenstein, Robbins et al. 1990; Studenski, Duncan et al. 1991; Province, Hadley et al. 1995) and other clinical populations (Richardson, Ching et al. 1992; Richardson and Hurvitz 1995). Walkasins™, a lower limb sensory prosthesis that replaces lost foot pressure sensation with vibrotactile feedback around the lower calf, can address this need.

A growing body of research has investigated the use of vibrotactile feedback to enhance balance control following short-term use. Vibrotactile displays have been used successfully by the U.S. Navy to provide navigational cues that allow blindfolded pilots to control their aircraft (Rupert 2000; Rupert 2000). Sensory substitution devices to aid balance have provided auditory (Chiari, Dozza et al. 2005; Dozza, Chiari et al. 2005; Dozza, Chiari et al. 2005; Dozza, Horak et al. 2007), electrotactile (Tyler, Danilov et al. 2003), and vibrotactile feedback (Wall, Weinberg et al. 2001; Wall, Merfeld et al. 2002; Wall and Weinberg 2003; Wall, Oddsson et al. 2004). More recent work has demonstrated the utility of vibrotactile feedback to improve postural control in patients (Horak, Dozza et al. 2009; Wall, Wrisley et al. 2009; Horak 2010; Wall 2010; Wall and Kentala 2010). None of these technologies, however, have been based on the measurement of foot pressure nor have they been intended to be worn on a continuous basis as a balance prosthetic device (Statler, Wrisley et al. 2007, Wall 2012). Current devices typically require a lab-engineer “on hand” to ensure functionality.

## Hypotheses and Objectives:

The purpose of this study is to investigate the effect of Walkasins (Figure 1), a new user-friendly and robust external lower limb sensory prosthesis developed by RxFunction Inc. under NIH funding through a Small Business Innovative Research grant, on the balance and gait of persons with peripheral neuropathy who also experience balance problems. Walkasins provide gentle vibrations to the skin around the lower leg that reflect changes in pressure under the foot sole indicating the state of balance. The user learns to use these vibrations to control balance.

We hypothesize that patients who use the Walkasins turned on will receive balance information that will improve their outcomes on gait and balance function, whereas patients who wear Walkasins turned off will not improve their outcomes on gait and balance function.

**Figure 1. The Walkasins incorporate a thin shoe insert that measures changes in foot pressure during body sway. Vibrations provided to the skin on the lower calf represent new sensory information that the patient learns to use to improve balance.**

PROTOCOL XXXX-X

The Effect of Walkasins on Balance and Gait in People with Peripheral Neuropathy

PI: [name]

Version Date: April 5, 2016

## **Research Subject Recruitment and Inclusion/Exclusion Criteria:**

In this study, we will recruit 30 Veterans who have been diagnosed with peripheral neuropathy and who have self-reported balance problems. The following inclusion and exclusion criteria will be used for the study:

### Inclusion criteria

- Age: 18-90 years, male or female,
- Self-reported difficulty with balance,
- Diagnosed with sensory peripheral neuropathy (inability to perceive 10 g monofilament on the plantar surface of the foot at the big toe, 5th and 1st metatarsal),
- Functional Gait Assessment (FGA) <23 or fail on test 1, 2 or 3 on the 4-Stage Balance Test),
- Ability to understand informed consent,
- Living in the community,
- Shoe size between 8.5" (women's 5) and 11.25" (men's 12).

### Exclusion criteria

- Inability to perceive vibration stimulation on the lower calf (e.g., inability to sense vibration from tuning fork on the calf),
- Use of ankle-foot orthosis for ambulation,
- Open wounds on the foot or calf,
- Musculoskeletal or other neurological conditions that impact gait and balance (for example total joint replacement, moderate to severe Parkinson's disease, stroke, etc.).

Fliers will be posted in the physical therapy gyms at the Minneapolis VA Health Care System to advertise the study. Subjects who see the flier will be asked directly about their interest in the study. Subjects will also be recruited by screening patient data within CPRS using the ICD-10 code for peripheral neuropathy. Subjects found in the screening process will first be contacted via a letter, and then called by the PI or a member of the study team to see if they are interested in participating in the study.

The study will involve one visit to the Minneapolis VA's Physical Therapy Department and should last between 2 to 3 hours. After arriving at the VA, the subject will go through the consent process with a member of the research staff. The consent process will happen within a private room in the Physical Therapy Department. Study staff will answer any questions related to the study and will ask the subject to answer questions that verify that they understand the study. After the consent process, the subjects will sign the appropriate forms indicating their consent to participate in the study and to allow the study team to use their data (explained in consent and HIPAA documents). After the consent process, the study staff will check the inclusion and exclusion criteria and will enroll the subject into the study if they meet all criteria.

## **Research Methodology:**

After enrollment into the study, subjects will complete a health screening questionnaire and the Activities-specific Balance Confidence Scale:

- Health Screening Questionnaire – Subjects will fill out a screening questionnaire to assess common health issues related to neurological, musculoskeletal, cardiopulmonary disorders, and other systemic diseases as well as information on falls and currently used medications.

PROTOCOL XXXX-X

[figure not shown]
The Effect of Walkasins on Balance and Gait in People with Peripheral Neuropathy

PI: [name]

Version Date: April 5, 2016

- Activities-Specific Balance Confidence (ABC) Questionnaire – Powell and Myers (1995) developed the Activities-Specific Balance Confidence (ABC) Scale in an effort to detect levels of balance confidence in elderly persons (see Appendix). The ABC scale is a one-page questionnaire that asks questions about balance confidence when performing 16 different tasks.

Subjects will then don the Walkasins device and complete baseline measures of the Functional Gait Assessment (FGA), 10 meter Gait Speed and 4-Stage Balance Test (see Figure 2 for protocol design). During baseline testing, the Walkasins will be turned off.

**Figure 2:** Cross-over study design.

- Functional Gait Assessment – The FGA is a reliable and valid measure of gait function related to postural stability and has been shown to be effective in classifying fall risk in older adults and predicting unexplained falls in community-dwelling older adults (Wrisley, Marchetti et al. 2004; Wrisley and Kumar 2010). It has also been validated in stroke survivors (Lin, Hsu et al. 2010) and patients with Parkinson’s disease (Leddy, Crowner et al. 2011) and it has less flooring and ceiling effect than the Dynamic Gait Index (Lin, Hsu et al. 2010). The FGA includes a 10 item scale where each item is scored from 0 to 3 (3=normal, 2=mild impairment, 1= moderate impairment, 0 = severe impairment). The maximum score is 30. A difference of 8 points between measurement times is defined as the MCID in persons with vestibular disorders (Marchetti and Whitney 2010).
- 10 meter Gait Speed – The 10m-walk (Perera, Mody et al. 2006) is routinely done in rehabilitation, has excellent reliability in chronic stroke patients (Hiengkaew, Jitaree et al. 2012) and physical therapists are well- trained in reliably performing this measure. In addition, gait speed has been found to be an important predictor of survival in older adults (Hardy, Perera et al. 2007), further emphasizing its importance as a clinical outcomes measure. Gait speed (10 meter walk using the middle 6 meters) will be assessed under two conditions: 1) instructed to walk at normal speed, 2) instructed to walk as fast as they can. A difference of 0.10m/sec is defined as the minimal clinically important difference (MCID) (Perera, Mody et al. 2006).

PROTOCOL XXXX-X

The Effect of Walkasins on Balance and Gait in People with Peripheral Neuropathy

PI: [name]

Version Date: April 5, 2016

- **4-Stage Balance Test** – The 4-Stage Balance Test is part of the CDC recommended test protocol for balance function (STEADI, [http://www.cdc.gov/steady/pdf/4-stage\\_balance\\_test-a.pdf](http://www.cdc.gov/steady/pdf/4-stage_balance_test-a.pdf)). It includes four gradually more challenging postures the subject is exposed to; 1) Stand with feet side by side; 2) Stand with feet in semi-tandem stance; 3) Stand with feet in tandem stance; 4) Stand on one leg. Subjects pass if they can hold the stance for 10 s and then move on to the next stance. A fail of 1, 2 or 3 indicates at risk of falling. In addition we will record time for each of the tests.

Subjects will then be randomized into two groups according to their gait function (as measured by the FGA) and use of an assistive device (normal use is permitted, but not during the research study). Group A will initially be trained and tested with the Walkasins turned on, then following a 60 minute break, will be trained and tested with the Walkasins turned off. Group B will initially be trained and tested with the Walkasins turned off, then following a 60 minute break, will be trained and tested with the Walkasins turned on. During testing, subjects will complete trials of Functional Gait Assessment, 10 meter Gait Speed and the 4-Stage Balance Test. All training and testing will be done by a physical therapist.

### **Data Analysis:**

The primary outcome measures of this study include the Functional Gait Assessment, 10 meter Gait Speed test, and the 4-Stage Balance Test. Using a between-group parametric statistical model, we will compare baseline measures from both groups to post-training outcomes following the first training session. We expect that Group A (i.e., the group that first trained with the Walkasins on) will have a statistically significant improvement in functional gait and balance measures compared to Group B (i.e., the group that first trained with the Walkasins off). We will also compare baseline measures to the post-training outcomes for Group A following the second training session (i.e., with the Walkasins off) to confirm that the 60 minute break between training sessions allowed for a washout effect of the first training. If we are able to confirm a washout effect, we will pool our data (n=30) to compare the outcome measures from baseline and post-training with the Walkasins turned on.

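### Three unranked primary outcomes, two with more than one candidate variable, have no alpha, order, adjustment or success rule, so the error rate of the primary claim is undefined

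*Combined protocol and SAP*

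**What the plan says.** Data Analysis lists the primary outcomes in one sentence and gives them equal standing: "The primary outcome measures of this study include the Functional Gait Assessment, 10 meter Gait Speed test, and the 4-Stage Balance Test". The main comparison is between the groups after the first training session, using a parametric model that is not specified further. The plan predicts that Group A "will have a statistically significant improvement in functional gait and balance measures compared to Group B". If washout is confirmed, "we will pool our data (n=30) to compare the outcome measures from baseline and post-training with the Walkasins turned on".

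Research Methodology describes how each outcome is measured:

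- **Functional Gait Assessment (FGA):** "The FGA includes a 10 item scale where each item is scored from 0 to 3", which gives one total with a maximum of 30.
- **Gait speed:** it "will be assessed under two conditions: 1) instructed to walk at normal speed, 2) instructed to walk as fast as they can".
- **4-Stage Balance Test:** "Subjects pass if they can hold the stance for 10 s and then move on to the next stance". The description ends: "In addition we will record time for each of the tests".

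Hypotheses and Objectives says that patients using the device turned on "will receive balance information that will improve their outcomes on gait and balance function", without separating the outcomes. The document gives no significance level, sidedness, test order, multiplicity adjustment or rule for how many outcomes must succeed.

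**The concern.** Two things are left open. The first is which variable represents gait speed and which represents the 4-Stage Balance Test. The second is what pattern of results counts as success.

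If one significant result is enough, the chance of a false claim exceeds the per-test level, and an isolated p<0.05 on one variable is hard to interpret. If all must be significant, there is no inflation, but power is lower than for one outcome. As written, the success rule, the walking condition and the balance score could all be settled after the results are known. With 30 participants and several candidate variables, that freedom weakens any positive finding.

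**Working it through.** The plan gives no alpha, power, effect size or sample-size derivation, so it has no figure of its own to reproduce. The calculation below shows how far the error rate depends on choices the plan does not make.

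**Inputs from the plan**
- Three primary outcomes (Data Analysis).
- Candidate variables (Research Methodology): FGA total, 1; gait speed, 2; 4-Stage Balance Test, at least 2 (pass/fail, and time taken as a single score). Total 1 + 2 + 2 = 5. Fixing one variable per outcome gives 3.
- 30 participants (recruitment section).

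**Assumptions, not in the plan**
- Two-sided 0.05 per test; equal allocation, 30/2 = 15 per group; equal correlation r between test statistics.
- Every score treated as normal, which a pass/fail score is not.
- For power, a true difference of 1.0 SD on each outcome.

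**Step 1: any one significant result counts.** With independent tests, the chance of at least one false positive is 1 − 0.95^k:
- k = 3: 1 − 0.8574 = 14.3%
- k = 4: 1 − 0.8145 = 18.5%
- k = 5: 1 − 0.7738 = 22.6%

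With correlation, write each statistic as √r·C + √(1−r)·E, where C is shared and E is specific to the test. Then integrate over C the probability that all k statistics lie within ±1.96, and subtract from 1:

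| Tests | r = 0 | r = 0.7 | r = 0.9 |
|---|---|---|---|
| 3 | 14.3% | 10.9% | 8.4% |
| 4 | 18.5% | 13.0% | 9.4% |
| 5 | 22.6% | 14.8% | 10.2% |

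Two-sample t simulations with 15 per group (k = 3 and 5, r = 0 and 0.9) agreed within 0.3 points. The range is therefore about 8% to 23%.

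**Step 2: all must be significant.** A false claim requires a significant result on at least one outcome with no true effect, so its probability cannot exceed 5%. The cost is power. For one outcome, the noncentrality is 1.0 × √(15/2) = 2.74 with 28 degrees of freedom, giving 75.3%. For three independent outcomes this is roughly 0.753³ = 0.427. Simulation gives:

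| Tests | r = 0 | r = 0.7 | r = 0.9 |
|---|---|---|---|
| 3 | 42.8% | 58.9% | 66.3% |
| 5 | 24.0% | 51.4% | 62.5% |

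**Step 3: Holm across three outcomes, one variable each.** Simulated per-outcome power is 67.8%, 65.7% and 64.8% at r = 0, 0.7 and 0.9, against 75.3% for one outcome tested alone. If only one of the three outcomes responds, power for it is 58.2% (r = 0 and 0.7).

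The conditional pooled comparison is not counted in any of these figures.

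**The case against.** The strongest reply is that the plan can be read as needing no adjustment. It joins the three measures with a conjunction and predicts improvement in the plural, and the hypothesis does the same. If all three had to succeed, the error rate would be at most 5%. A reader might go the other way and infer that the plan has an inflated error rate, for example 14% or 23%. The documents do not support that, because inflation arises only if any one result counts and the plan does not adopt that rule. Nor do they commit to the all-outcomes rule: the sentence on significance states what the team expects, not how success will be judged. What stands is that the rule is missing.

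Four narrower points also limit the concern:

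- Gait speed might be described as scored two ways. It is one measure taken under two walking conditions.
- The text gives some cues to the balance score. A parametric model fits times better than pass/fail, while time is introduced as an addition to pass/fail. These cues point in opposite directions and settle nothing.
- The pooled comparison might be taken as another primary test. The plan places it after the between-group comparison and makes it conditional on washout, so it reads as a follow-on. Its label is still missing.
- Holm might appear to cost nothing because power to win on at least one of three outcomes is 92.7% (r = 0) or 76.7% (r = 0.7), above 75.3%. That sets success on any outcome against success on one named outcome. Like for like, per-outcome power falls.

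The study is small and takes a single visit, which argues for a light remedy. But the document does not call it a pilot or exploratory, and it predicts a statistically significant difference between randomised groups.

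**Conclusion.** The concern holds as an unspecified success rule and unspecified primary variables. The error rate of the primary claim cannot be stated from the plan: about 8% to 23% if any one of three to five tests counts, and at most 5% if all must be significant. The lower end is three tests at correlation 0.9 and the upper end five independent tests. Both ends rest on the assumed two-sided 0.05 per test, equal correlations and normal scores. The power figures also assume 15 per group and 1.0 SD on each outcome.

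The absence of the rule follows from the text and needs none of these assumptions. It does not invalidate the design, but it should be corrected, because it leaves the primary claim open to selection after the results are seen.

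**What to change.** Amend Data Analysis before data are seen:

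1. State alpha and whether tests are two-sided.
2. Name one variable (one outcome, with one condition or score) as the single primary for the Group A versus Group B comparison after the first session. The choice belongs to the trial team; the FGA total is one option.
3. Fix one variable for each of the other two outcomes. Once the primary is significant, test them as secondaries in a stated order or with Holm.
4. Label the conditional pooled comparison as supportive.

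Keeping all three as primary stays closest to the present text and is equally valid. In that case, fix one variable for each, then either require all three to be significant, with no adjustment, or let any one suffice with Holm across the three.

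The change needs a few sentences and no new data. With a single primary, a result on another outcome alone is no longer a primary success. Requiring all three lowers power to about 43% to 66%, depending on correlation. Holm lowers per-outcome power from about 75% to about 65–68%, or to about 58% if only one outcome responds. These power figures carry the assumptions listed in the working.

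### The first-session comparison states no adjustment for baseline or the allocation factors; run as an unadjusted change score it is unbiased, but loses precision unless the baseline slope is near 1

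*Combined protocol and SAP*

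**What the plan says.** The Data Analysis section makes FGA, 10 m gait speed and the 4-Stage Balance Test primary, and covers all three with one sentence: "Using a between-group parametric statistical model, we will compare baseline measures from both groups to post-training outcomes following the first training session". It then expects Group A to improve more than Group B. It does not name the test, the dependent variable (change, post-training value or group-by-time), a baseline covariate or any allocation term. No other section does so.

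The Research Methodology section has subjects, before randomisation, "complete baseline measures of the Functional Gait Assessment (FGA), 10 meter Gait Speed and 4-Stage Balance Test". It then states: "Subjects will then be randomized into two groups according to their gait function (as measured by the FGA) and use of an assistive device". No FGA cut-point, block structure or allocation ratio is given. The sample is 30 subjects.

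For the 4-Stage Balance Test the same section gives a pass/fail rule, "Subjects pass if they can hold the stance for 10 s and then move on to the next stance", treats failure of any of the first three stances as a marker of fall risk, and adds "In addition we will record time for each of the tests". No section says which of these forms is analysed.

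**The concern.** The design treats FGA and assistive-device use as important enough to govern allocation, yet the analysis mentions neither. The first-session contrast is the only randomised comparison in the plan that is free of carry-over. It has about 15 subjects per group (inferred from 30, since no ratio is stated), so precision matters.

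A change score fixes the baseline slope at 1. If the true slope differs, baseline variation that a covariate would remove stays in the error term. What is at stake is power and the width of the confidence interval, not validity.

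Separately, a primary outcome with several possible forms and no stated choice lets the form be picked after the data are seen.

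**Working it through.** **Inputs.** From the documents: N = 30, two groups, baseline of all three outcomes taken before randomisation, allocation by FGA and device use. The documents give no alpha, SD, correlation, effect size or power, so there is no plan figure to reproduce.

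Assumed: 15 per group, two-sided 5%, normal outcomes, effect 0.7 baseline SD, and added covariates that are not prognostic beyond the outcome's own baseline. Let ρ be the baseline–post correlation and k the post SD divided by the baseline SD, so that b = ρk.

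**Step 1: closed form, simple allocation.** In units of Var(baseline):

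- Change score: 1 + k² − 2ρk
- ANCOVA with q covariates: k²(1 − ρ²) × (N − 3)/(N − 3 − q)
- Difference before the small-sample factor: (1 − ρk)² = (1 − b)², which is zero only at b = 1

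The small-sample factor is 27/26 = 1.038 for q = 1, 27/25 = 1.080 for q = 2 and 27/24 = 1.125 for q = 3.

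Example, k = 1 and ρ = 0.5: 1.00/0.75 = 1.333, and 1.333/1.038 = 1.28.

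Variance ratio, change score over ANCOVA, own baseline only (below 1 means ANCOVA loses):

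| k | ρ 0.5 | 0.7 | 0.8 | 0.9 |
|---|---|---|---|---|
| 0.8 | 1.69 | 1.53 | 1.50 | 1.58 |
| 1.0 | 1.28 | 1.13 | 1.07 | 1.01 |
| 1.2 | 1.11 | 1.00 | 0.97 | 0.99 |

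**Step 2: FGA with stratified allocation, by simulation.** Allocation was assumed to alternate within four strata (FGA above or below the median, by device use, 40% users). ANCOVA used baseline FGA and device use. There were 8,000 trials per setting, with Monte Carlo error of about ±1.1 points. Power in %, change score vs ANCOVA:

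| k | ρ 0.5 | 0.7 | 0.8 | 0.9 |
|---|---|---|---|---|
| 0.8 | 52 vs 75 | 76 vs 90 | 90 vs 97 | 99 vs 100 |
| 1.0 | 45 vs 56 | 67 vs 72 | 84 vs 86 | 99 vs 99 |
| 1.2 | 38 vs 42 | 57 vs 58 | 73 vs 71 | 94 vs 93 |

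**Step 3: why the FGA test becomes conservative.** Stratifying on FGA balances baseline between groups, which reduces the true variance of the change-score difference. The t-test's standard error still contains the full (1 − b)² term, so it is too large. With no true effect, the change-score test rejected 3.6% of the time at k = 1.0, ρ = 0.5, and 2.5 to 2.7% at k = 0.8. At b = 1.5 × 0.95 ≈ 1.42 it rejected between 2 and 3%, so the effect occurs on both sides of b = 1. Under simple 15:15 allocation it rejected 4.6 to 5.3%.

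**Step 4: where ANCOVA costs.** Take k = 1.2 and ρ = 0.8, so b = 0.96. The raw ratio is 0.52/0.5184 = 1.003. With three covariates (gait speed, simple allocation) it is 1.003/1.125 = 0.89, so ANCOVA's variance is 1/0.89, or about 12%, higher, and power is 73% for the change score vs 68% for ANCOVA. Under stratified allocation at k = 1.2 and ρ 0.7 to 0.9, ANCOVA's variance is about 0 to 2% higher for FGA and 3 to 5% higher for gait speed (gait-speed baseline assumed to correlate 0.6 with FGA).

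**Step 5: the 4-Stage Balance Test.** No arithmetic applies. The number of stances passed takes five values (0 to 4), the risk marker takes two, and times are judged against a 10 s hold. These are different variables needing different models, and the Data Analysis section selects none.

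**The case against.** The strongest reply is that the loss is doubly conditional. The plan does not commit to a change score, since its wording also admits ANCOVA or a mixed model, and no section supplies a slope. This stands: a reader might infer that the plan has chosen an inefficient analysis, but the text shows only that nothing is specified.

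Next, all testing falls in one visit that "should last between 2 to 3 hours", so ρ may be high. With equal SDs and ρ near 0.9 the gain is almost nil, and the fuller covariate set can lose. This also stands as a limit. It is not general: at k = 0.8 the ratio rises from 1.50 to 1.58 as ρ goes from 0.8 to 0.9.

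A reader might also infer that the entry rule narrows baseline FGA, raises k and so removes the gain. The rule is "Functional Gait Assessment (FGA) <23 or fail on test 1, 2 or 3 on the 4-Stage Balance Test", so FGA need not be below 23. Restricting the baseline range also lowers ρ as it raises k, and leaves a linear slope unchanged.

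Two stronger readings fail. One is bias or an inflated false-positive rate: under randomisation a prespecified change score is unbiased and at worst conservative. The other is that a parametric model is wrong for the 4-Stage Balance Test: logistic and proportional-odds models are parametric. That later stances lack times after a failure is an inference, because the protocol says a time is recorded for each test.

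**Conclusion.** The concern holds as a conditional loss of efficiency. The plan states no adjustment for baseline or for the factors it randomises on. If the first-session comparison is run as an unadjusted change score, ANCOVA would gain about 11 points of FGA power at ρ = 0.5 with equal SDs (45 to 56%) and about 23 points at ρ = 0.5 with k = 0.8 (52 to 75%). There is essentially no gain when b is near 1, for example equal SDs with ρ about 0.9, or k = 1.2 with ρ about 0.8. These figures rest on the assumptions listed above. The sponsor should make the change, because the slope is unknown and, in the stratified FGA case, the possible gain far exceeds the possible loss of about 2 points. Confidence in the size is medium. The 4-Stage point is a clarification with no figure attached.

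**What to change.** In the Data Analysis section, specify the first-session analysis of FGA total and of gait speed (normal and fast pace) as an ANCOVA of the post-training value on group, with that outcome's own baseline as covariate plus the factors actually used in allocation (baseline FGA and assistive-device use). One FGA term serves both purposes when FGA is the outcome. Report the adjusted difference with its 95% CI. State how the allocation uses the two factors. If it is not in fact stratified on them, own baseline alone is enough.

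For the 4-Stage Balance Test, name one analysed form and a matching method. One option is the number of stances passed (0 to 4) with an ordinal or rank method that takes account of the baseline result.

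The cost is wording only, since all baselines are already collected before randomisation. ANCOVA spends one degree of freedom (own baseline only), two (FGA) or three (gait speed). If the slope is near 1 and the added covariates are not prognostic, variance rises by 0 to 5% under stratified allocation, and by up to about 12% for the three-covariate gait-speed model under simple allocation.

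### The washout check that decides whether the n=30 analysis is run measures carry-over, practice, device-off training and fatigue together, and the plan gives no criterion for passing it

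*Combined protocol and SAP*

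**What the plan says.** The Research Subject Recruitment section sets the sample: "we will recruit 30 Veterans who have been diagnosed with peripheral neuropathy". Under Research Methodology, baseline is measured once, before randomisation and before any training, with the device worn but inactive: "During baseline testing, the Walkasins will be turned off". Group A is trained and tested with the device on, "then following a 60 minute break, will be trained and tested with the Walkasins turned off". Group B has the reverse order. The outcome tests are repeated in each session. No second baseline after the break is described.

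Data Analysis then has three steps:

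1. A comparison of the two groups on change from baseline to the end of the first session. No condition is attached to it.
2. A comparison within Group A of baseline with the device-off result after the second session, "to confirm that the 60 minute break between training sessions allowed for a washout effect of the first training".
3. A conditional step: "If we are able to confirm a washout effect, we will pool our data (n=30", comparing baseline with the device-on result across both groups.

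The section gives no test, significance level, margin or threshold for step 2. It does not say what follows if the three primary outcomes disagree, and step 2 uses none of Group B's scores.

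**The concern.** Step 2 is meant to isolate what the first training leaves behind after the break. Group A's last score, however, comes after a second round of therapist-led training and a further repetition of every test, late in a visit of two to three hours. Its difference from an untrained baseline mixes several effects, and some may have opposite signs. Practice could make the check fail when the device leaves nothing behind. Fatigue could make it pass when carry-over is real. A larger sample would not cure this.

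A second difficulty is the word *confirm*. Without a margin, the obvious working rule is that no significant change means washout. In a group of about 15, that would treat lack of evidence as evidence of absence.

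At stake are the statement that 60 minutes is an adequate washout and the decision whether to run the n=30 analysis.

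**Working it through.** The plan states no power, SD, alpha or margin for this comparison, so there is no figure of its own to reproduce.

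**Inputs.** From the documents: 30 subjects, the two sequences, one untrained device-off baseline, and reference differences of 0.10 m/s for gait speed and 8 points for the FGA (the latter from vestibular disorders). Assumed: 15 subjects in Group A (the allocation ratio is not stated; 12 to 18 also checked), a two-sided 5% paired t-test, and SDs of change as shown.

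**Step 1: what each comparison measures.** Write each score as a change from baseline. Let P1 and P2 be the shared effect of practice, training and fatigue by sessions 1 and 2. Let T be the effect of the device being on, and C_on and C_off the carry-over from a first session with the device on or off.

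| | Session 1 | Session 2 |
|---|---|---|
| Group A (on, then off) | P1 + T | P2 + C_on |
| Group B (off, then on) | P1 | P2 + T + C_off |

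- Washout check (A, session 2): P2 + C_on. It equals C_on only if P2 is zero.
- First-session comparison (A minus B): (P1 + T) − P1 = T. No carry-over term.
- Pooled comparison of baseline with device on, equal groups: [(P1 + T) + (P2 + T + C_off)]/2 = T + (P1 + P2 + C_off)/2. C_on does not appear; practice does.

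So the check targets C_on, measures P2 + C_on, and controls an analysis that C_on does not enter.

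**Step 2: precision with n = 15.** Power comes from the non-central t distribution with 14 degrees of freedom and non-centrality d√15, where d is the true net change in SD units.

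- d = 0.3: non-centrality 1.16, power 0.192, missed 81% of the time.
- d = 0.5: non-centrality 1.94, power 0.438, missed 56%.
- d = 0.75: non-centrality 2.90, power 0.771.
- 95% half-width: t(0.975, 14)/√15 = 2.145/3.873 = 0.55 SD.
- Change detectable with 80% power: 0.78 SD.

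The same powers apply if the net change is all practice and C_on is zero: the check then fails 44% of the time at 0.5 SD and 77% at 0.75 SD.

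For Group A sizes of 12 and 18, the miss rate at 0.5 SD is 65% and 48%, and the half-width 0.64 and 0.50 SD.

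**Step 3: against the protocol's reference differences (n = 15).** A true net change of 0.10 m/s is missed 5%, 33%, 56% and 70% of the time for an SD of change of 0.10, 0.15, 0.20 and 0.25 m/s. At SD 0.20 the half-width is 0.554 × 0.20 = 0.11 m/s, wider than the reference difference. For the FGA with an assumed SD of 3, the half-width is 0.554 × 3 = 1.7 points. An 8-point net change would be detected; a 2-point one would be missed 33% of the time.

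**Step 4: opposing effects.** With carry-over of +2 FGA points and fatigue of −2, the net change is zero and the check finds a difference only 5% of the time. This follows by construction and is an illustration, not an estimate of fatigue.

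**The case against.** The strongest reply is that the main analysis does not depend on this check. The randomised first-session comparison comes first, carries the expected significant result and is run whatever the check shows. That stands. A reader might infer that the plan chooses between a first-session and a pooled analysis according to the check, but pooling is an additional step and replaces nothing.

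Three further points stand in part.

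- The plan does not make a non-significant p-value its criterion. It gives none, and an interval could be judged against the reference differences it quotes. The claim is therefore only that a non-significant result *could* be read as washout.
- A reader might infer that wrongly declaring washout biases the pooled estimate through carry-over. It does not: Group A's device-on score precedes its device-off session, and Group B's follows only device-off training.
- Failing the check because of practice may be protective, since practice also inflates Group B's device-on score against baseline, and the text speaks of washout of the first training in general. But Group A's change also contains the second session's own training and practice, which are not residue of the first.

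It is also fair that a two-group carry-over contrast is much less precise than the present check. The gain is in what is estimated, not in precision.

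**Conclusion.** The point holds as a should-fix. Group A's change from baseline cannot separate carry-over from practice, device-off training and fatigue, so it cannot establish that 60 minutes washed out the first training. That conclusion needs no assumed figure. The size of the precision problem does depend on assumptions: a 1:1 split and a two-sided 5% paired t-test give a 56% chance of missing a net change of 0.5 SD and a half-width of 0.55 SD. Group sizes of 12 to 18 do not alter the conclusion.

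The consequences are limited to the washout statement and the decision to pool. It would go too far to say that the trial's main randomised comparison is compromised, or that the check carries no information: under the assumed FGA SD of 3 it could exclude a net change as large as 8 points. The pooled step has its own weakness, practice in an uncontrolled comparison with baseline, and passing the check would not remove it.

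**What to change.** In Data Analysis:

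1. Delete the conditional rule and the word *confirm*.
2. State that the confirmatory conclusion rests on the randomised first-session comparison.
3. Run the two-session crossover analysis (device on versus off, with period and sequence terms) whatever the carry-over result, and label it supportive. In the notation above, half of (A1 − A2) − (B1 − B2) is T − (C_on − C_off)/2, so it can still be affected by carry-over.
4. Report carry-over descriptively from both groups, using changes from baseline: (A session 1 + A session 2) − (B session 1 + B session 2). The device and shared session effects cancel, leaving C_on − C_off. Give a 95% interval with no pass/fail reading.

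**Cost.** Rewording only: all the scores are already planned. The n=30 result becomes supportive. The carry-over interval will be wide: with 15 per group, SD of change 3 FGA points and correlation r between a subject's two changes (all assumed), the half-width is t(0.975, 28) × 3√[2(1 + r)] × √(2/15). For r = 0.3 this is 2.048 × 4.84 × 0.365 = 3.6 points; for r = 0.7, 2.048 × 5.53 × 0.365 = 4.1 points. The contrast estimates only the difference between device-on and device-off carry-over, and it cannot be separated from sequence or treatment-by-period effects. The report should say so.
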